### 5.2.1 Visit 1 (Day -14 to -1); Screening

The following procedures will be performed at Visit 1 (Screening):

- Obtain written informed consent (before start of any study related procedures that are not standard of care) including optional consents for additional future analyses (Note: informed consent may be obtained up to -28 days to allow flexibility in scheduling of the screening procedures).
- Evaluate all inclusion and exclusion criteria to ensure that patients meet all inclusion criteria and none of the exclusion criteria.
- Review medical history including all previous cancer treatments.
- Record prior (within previous 28 days) and concomitant medications including start/stop dates, indication, dose and frequency.
- Record demographic data including date of birth, age, gender, race, ethnicity and smoking status.
- Measure and record height and weight.
- Perform and record physical examination.
- Assess and record performance status (ECOG) within 7 days before start of treatment.
- Record vital signs. Measure body temperature, systolic/diastolic blood pressure (BP) and pulse rate.
- Collect blood for a serum pregnancy test for female patients who are not postmenopausal or surgically sterile.
- Assess and record current disease status (computed tomography [CT] or other measurements to be defined). This may be performed within 28 days before start of treatment (Visit 2).
- Collect blood samples for blood chemistries, hematology and creatinine clearance (In all instances throughout the study, when creatinine clearance is calculated, the Cockcroft-Gault formula should be used.) within 7 days before start of treatment, analyze, review and report any clinically significant abnormalities to medical monitor before dosing.
- Perform and record ophthalmology examination.

- Obtain a 12-lead electrocardiogram (ECG), ECHO cardiogram or MUGA for LVEF.
- Collect urine samples for urinalysis within 7 days before start of treatment.
- For patients enrolled in Part 2 of the study, a tumor biopsy and blood may be required to obtain tumor genetic information required to confirm eligibility (e.g., BRAF, MEK, RAS, or ERK mutation).
- For patients who have given consent for optional research tests involving the collection of tumor tissue and plasma samples for circulating tumor DNA analysis, collect tumor biopsy and plasma samples prior to first dose of BVD-523.

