2.3 STUDY ENDPOINTS

2.3.1 Primary Endpoints

Safety

- Evaluation of the DLTs of BVD-523
- Determination of MTD of BVD-523
- Determination of RP2D of BVD-523
- Evaluation of treatment-related AEs of BVD-523

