10.2 ADVERSE EVENTS

An adverse event is defined as any untoward medical occurrence in a patient administered a medicinal product that does not necessarily have a causal relationship with this treatment. This includes an exacerbation of pre-existing conditions or events, inter-current illnesses, drug interaction, or the significant worsening of the indication under investigation that is not recorded elsewhere in the eCRF under specific efficacy assessments. The reporting period of an AE begins from the time that the patient provides informed consent through and including 30 calendar days after the last administration of BVD-523 (or at the time when a patient begins a new anti-cancer therapy). Anticipated fluctuations of pre-existing conditions, including the disease under study that does not represent a clinically significant exacerbation or worsening, need not be considered AEs.

The severity of an AE will be graded according to the National Cancer Institute (NCI) Common Terminology Criteria for Adverse Events (CTCAE), version 4 with values of Grade 1 to Grade 5 (increased in severity). For AEs not covered by NCI CTCAE, the severity will be characterized as “mild,” “moderate,” or “severe” according to the following definitions:

- Mild (equivalent to Grade 1) events are usually transient and do not interfere with the patient’s daily activities.
- Moderate (equivalent to Grade 2) events introduce a low level of inconvenience or concern to the patient and may interfere with daily activities.
- Severe (equivalent to Grade 3) events interrupt the patient’s usual daily activities.

All AE relationship to the study drug, BVD-523, are classified as “unrelated,” “possibly related,” or “related.”

AE Coding

Any AE including SAE in verbatim term will be coded in accordance with the Medical Dictionary for Regulatory Activities (MedDRA®) dictionary version 16.0 to a system organ class (SOC) and preferred term (PT) within each SOC. Analysis of AEs will then be performed using SOCs and PTs.

Dose Limiting Toxicities, Maximum Tolerated Dose, and Recommended Phase 2 Dose

As specified in Section 2.1.1, a DLT for Part 2 is defined (per definition in protocol amendment 7) as a **BVD-523 related toxicity in the first 21 days** of treatment that results in:

- \geq Grade 4 hematologic toxicity for > 1 day;
- Grade 3 hematologic toxicity with complications e.g., thrombocytopenia with bleeding;

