- \geq Grade 3 non-hematologic toxicity, except untreated nausea, vomiting, constipation, pain, and rash (these become DLTs if the AE persists despite adequate treatment), a doubling of AST/ALT in patients with grade 2 ALT/AST at baseline;
- A treatment interruption exceeding 5 days (or an interruption exceeding 7 days for rash, despite adequate treatment) in Cycle 1 (or inability to begin Cycle 2 for > 7 days) due to BVD-523-related toxicity³.

As specified in Section 2.1.1, the MTD is defined as the highest dose level at which $\leq 33\%$ of patients experience BVD-523 related DLTs in the first 21 days of treatment. The RP2D may be as high as the MTD and will be determined in discussion with the Clinical Investigators, the Medical Monitor, and the Sponsor. Observations related to pharmacokinetics (PK), pharmacodynamics (PD), and any cumulative toxicity observed after multiple cycles may be included in the rationale supporting the RP2D. Pharmacokinetic, pharmacodynamics, and/or Holter measurements may be suspended pending review of accumulated patient experience.

Treatment Emergent Adverse Event

A treatment emergent adverse event (TEAE) is any AE temporally associated with the use of BVD-523 (from BVD-523 initiation until 30 calendar days after the last administration of BVD-523), whether or not considered related to the study drug. If the onset of an AE is missing and the AE resolution date is either after the initial BVD-523 dose date or missing, then the AE will be considered treatment emergent.

AE Summaries

A subject who reported multiple AEs that map to a common PT or SOC is counted only once for that PT or SOC at the highest severity reported and at the greatest relationship to study drug.

The number and percentage of subjects who experienced at least one AE will be tabulated by SOC and PT with respect to dose level/treatment group for each study part. The same tabulation will also be applied to any SAE, any AE leading to premature discontinuation from the study, treatment emergent AEs and treatment-emergent SAEs.

³ For Amendments 1 and 2: A treatment interruption exceeding 3 days in Cycle 1 due to drug-related toxicity (or inability to begin Cycle 2 for > 7 days) due to drug-related toxicity.

For Amendment 3: A treatment interruption exceeding 5 days in Cycle 1 due to drug-related toxicity (or inability to begin Cycle 2 for > 7 days due to drug-related AE)

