For Amendments 4, 5, and 6: A treatment interruption exceeding 5 days (or an interruption exceeding 7 days for rash, despite adequate treatment) in Cycle 1 (or inability to begin Cycle 2 for > 7 days) due to BVD-523-related toxicity.

The number and percentage of subjects who experienced at least one AE will also be tabulated by SOC and PT within each dose level/treatment group with respect to relationship to study drug (unrelated, possibly related, and related) and severity (Grade 1 to Grade 5). Subject listings will also be provided for all AEs, all SAEs, all AEs leading to early discontinuation from the study and all AEs leading to study drug interruptions and length of interruptions.

Bar graphs of AEs in CTCAE Term will be displayed in decreasing order of incidence from most common to least common. Each bar in the plot will represent an AE in CTCAE Term. Severity of AE (grades) will be embedded in each bar using the percentages of patients in each AE grade. These plots will be provided for all AE tables produced.

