14 TABLE OF CONTENTS FOR DATA DISPLAYS

TFL Shells are included as stand-alone documents.

Tables/Figures

Part I

Part I: Study Population

Part I - Table 14.1.1.1	Subject Disposition	ITT Population
Part I - Table 14.1.1.2	Analysis Population	ITT Population
Part I - Table 14.1.2	Protocol Deviations	ITT Population
Part I - Table 14.1.3.1	Demographic and Baseline Characteristics	Safety Population
Part I - Table 14.1.3.2	Demographic and Baseline Characteristics	ITT Population
Part I - Table 14.1.4.1	Prior Medications	Safety Population
Part I - Table 14.1.4.2	Concomitant Medications	Safety Population
Part I - Table 14.1.4.3	Concomitant Medication Taken for Adverse Events	Safety Population
Part I - Table 14.1.5.1	Treatment Compliance	Safety Population
Part I - Table 14.1.5.2	Exposure to Study Drug	Safety Population
Part I - Table 14.1.6	Pregnancy Test Results	Safety Population

Part I: Efficacy

Part I - Table 14.2.1	Target Lesion Response per RECIST 1.1	PP Population
Part I - Table 14.2.2	Non-Target Lesion Response per RECIST 1.1	PP Population
Part I - Table 14.2.3	New Lesion	PP Population
Part I - Table 14.2.4	Overall Response per RECIST 1.1	PP Population
Part I - Table 14.2.5	Best Overall Response per RECIST 1.1	PP Population
Part I - Table 14.2.6	Best Overall Response by Disease and Mutation Status	PP Population
Part I - Table 14.2.7	Duration of Best Overall Response by Disease and Mutation Status	PP Population

Part I: Safety

Part I - Table 14.3.1.1	Dose Limiting Toxicities	Safety Population
Part I - Table 14.3.1.2	Details of Dose Limiting Toxicities	Safety Population
Part I - Table 14.3.1.3	Doses Selected as MTD and RP2D	Safety Population
Part I - Table 14.3.1.4.1	Frequency and Reasons for Dose Delays/Interruptions	Safety Population
Part I - Table 14.3.1.4.2	Duration of Dose Delays/Interruptions	Safety Population
Part I - Table 14.3.1.5	Adverse Events	Safety Population
Part I - Figure 14.3.1.5	Bar Graph of Adverse Events	Safety Population
Part I - Table 14.3.1.6	Serious Adverse Events	Safety Population
Part I - Figure 14.3.1.6	Bar Graph of Serious Adverse Events	Safety Population
Part I - Table 14.3.1.7	Adverse Events Leading to Premature Discontinuation from the Study	Safety Population
Part I - Figure 14.3.1.7	Bar Graph of Adverse Events Leading to Premature Discontinuation from the Study	Safety Population
Part I - Table 14.3.1.8	Adverse Events by Relationship to Study Drug	Safety Population

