Part I - Table 14.3.1.9	Adverse Events by Severity	Safety Population
Part I - Table 14.3.2.1	Treatment Emergent Adverse Events	Safety Population
Part I - Figure 14.3.2.1	Bar Graph of Treatment Emergent Adverse Events	Safety Population
Part I - Table 14.3.2.2	Serious Treatment Emergent Adverse Events	Safety Population

Part I: Death Narratives

Part I: Laboratory Results

Part I - Table 14.3.4.1	Laboratory Evaluations – Hematology	Safety Population
Part I - Table 14.3.4.2	Laboratory Evaluations – Clinical Chemistry	Safety Population
Part I - Table 14.3.4.3	Laboratory Evaluations – Urinalysis	Safety Population

Part I: Physical Examination Results

Part I - Table 14.3.5.1	Physical Examinations	Safety Population
Part I - Table 14.3.5.2	ECOG Performance Status	Safety Population
Part I - Table 14.3.5.3	Electrocardiograms	Safety Population
Part I - Table 14.3.5.4	Categorized Electrocardiograms	Safety Population
Part I - Table 14.3.5.5	Ophthalmology Examinations	Safety Population
Part I - Table 14.3.5.6	Vital Signs	Safety Population

Part I: Pharmacokinetics

Part I - Table 14.4.1	Pharmacokinetic Parameters Calculated from Blood Samples	PK Population
Part I - Table 14.4.2	Pharmacokinetic Parameters Calculated from Urine Samples	PK Population

Part I: Pharmacodynamics

Part I - Table 14.5.1	Fluid Pharmacodynamics	Pharmacokinetics Population
-----------------------	------------------------	-----------------------------

Part I: Tumor Genotyping

Part I - Table 14.6.1	Tumor Genetic Information	PP Population
-----------------------	---------------------------	---------------

Part II

Part II: Study Population

Part II - Table 14.1.1.1	Subject Disposition	mITT Population
Part II - Table 14.1.1.2	Analysis Population	mITT Population
Part II - Table 14.1.2	Protocol Deviations	mITT Population
Part II - Table 14.1.3.1	Demographic and Baseline Characteristics	Safety Population
Part II - Table 14.1.3.2	Demographic and Baseline Characteristics	mITT Population
Part II - Table 14.1.4.1	Prior Medications	Safety Population
Part II - Table 14.1.4.2	Concomitant Medications	Safety Population

Part II - Table 14.1.4.3	Concomitant Medication Taken for Adverse Events	Safety Population
Part II - Table 14.1.5.1	Treatment Compliance	Safety Population
Part II - Table 14.1.5.2	Exposure to Study Drug	Safety Population
Part II - Table 14.1.6	Pregnancy Test Results	Safety Population
Part II: Efficacy		
Part II - Table 14.2.1	Target Lesion Response per RECIST 1.1	PP Population

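### The AE tables by relationship and by severity include events from before the first dose, and no treatment-emergent version of either table is planned

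*SAP*

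**What the plan says.** SAP 10.2 sets two windows. For AEs, "The reporting period of an AE begins from the time that the patient provides informed consent", and it closes 30 days after the last dose or when new anti-cancer therapy starts. The TEAE window runs "from BVD-523 initiation until 30 calendar days after the last administration of BVD-523". Protocol 5.2.1 puts screening at Day -14 to -1 but adds that "informed consent may be obtained up to -28 days".

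Under AE Summaries, SAP 10.2 plans a plain incidence table by system organ class (SOC) and preferred term (PT) for all AEs. It repeats that table for SAEs, AEs leading to discontinuation, TEAEs and treatment-emergent SAEs. The finer tabulation is worded differently: subjects "who experienced at least one AE will also be tabulated by SOC and PT within each dose level/treatment group", by relationship and by Grade 1 to 5. It is not repeated for TEAEs.

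The display list in SAP 14 agrees. "Adverse Events by Relationship to Study Drug" is Part I Table 14.3.1.8 and Part II Table 14.3.1.7. "Adverse Events by Severity" is Part I Table 14.3.1.9 and Part II Table 14.3.1.8. The Part II bar graphs by relationship (Figures 14.3.1.8.1 and 14.3.1.8.2) are also titled as AEs or SAEs. The TEAE displays (Tables 14.3.2.1 and 14.3.2.2, Figure 14.3.2.1) have no relationship version and no severity table.

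**The concern.** The relationship and severity tables are the main tabular description of toxicity by dose level and by Part 2 group. A reader takes an event shown under a dose level to have occurred on that dose. As specified, a disease symptom or biopsy complication that arose after consent but before the first capsule is shown in the same cell as an on-drug event.

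The counting rule adds to this. Within a patient, each PT and each SOC is counted once, at the worst grade reported and the strongest relationship. Nothing limits the rule to events after dosing, so a screening event can set the grade that is displayed. Part 1 cohorts hold 1 to 6 patients and Part 2 groups up to 15, so a single patient is visible in the percentages.

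**Working it through.** **Step 1. Which events enter which display**

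| Display | Event set | Population |
|---|---|---|
| Plain SOC/PT incidence | All AEs, and repeated for TEAEs | Safety |
| By relationship | All AEs only | Safety |
| By severity, table | All AEs only | Safety |
| Graded bar graph | All AEs, and TEAEs (Figure 14.3.2.1) | Safety |
| Bar graphs by relationship (Part II) | All AEs and SAEs only | Safety |

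The Safety Population (SAP 5.1) is everyone who received at least one dose. It removes patients who were never dosed. It does not remove the pre-dose events of patients who were dosed.

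**Step 2. How a pre-dose event changes a cell**

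- Same PT: Grade 3 in screening and Grade 1 on drug gives one patient at Grade 3 under that dose level.
- Same SOC, different PT: the PT row shows the pre-dose event, and the SOC row shows its grade if that grade is the higher.
- Relationship table: a pre-dose event should be judged unrelated, so it adds to the unrelated rows unless the patient also has a more strongly related event of the same term.

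**Step 3. Share of the AE window before dosing (calendar time, not an event rate)**

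Share = pre-dose days / (pre-dose days + days on drug + 30).

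| Days on drug | 14 pre-dose days | 28 pre-dose days |
|---|---|---|
| 21 (one cycle) | 14/65 = 22% | 28/79 = 35% |
| 42 (to first scan) | 14/86 = 16% | 28/100 = 28% |
| 126 (six cycles, assumed) | 14/170 = 8% | 28/184 = 15% |

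**Step 4. Patients with a pre-dose Grade 3+ event**

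The documents give no background rate. Assume a rate r per 21 days, constant over time, with every event recorded and every such patient still dosed. Then P = 1 − (1 − r)^(d/21).

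| r per 21 days (assumed) | d = 14 | d = 28 |
|---|---|---|
| 2% | 1 − 0.98^(14/21) = 1.3% | 1 − 0.98^(28/21) = 2.7% |
| 5% | 1 − 0.95^(14/21) = 3.4% | 1 − 0.95^(28/21) = 6.6% |
| 10% | 1 − 0.90^(14/21) = 6.8% | 1 − 0.90^(28/21) = 13.1% |

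In a Part 2 group of 15, the expected number is 15 × 1.3%, 3.4% or 6.8% = 0.2, 0.5 or 1.0 patients over 14 days. Over 28 days it is 15 × 2.7%, 6.6% or 13.1% = 0.4, 1.0 or 2.0. One patient is 1/15 = 7 percentage points in such a group and 1/6 = 17 points in a cohort of 6. Only events whose term had a lower grade, or did not occur, on drug would change the severity table.

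**The case against.** The strongest reply is that few pre-dose events will reach these tables.

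- The schedule of assessments (Protocol Table 6.1, repeated in SAP 3.2) has no AE mark at screening, and Protocol 5.2.2 lists AE assessment after the first dose.
- Protocol 6.4 sends physical findings from before the start of drug to the medical history form. Protocol 9.1 excludes expected fluctuations of the disease.
- Protocol 4.3 and 4.4 require ECOG 0 or 1 within 72 hours of treatment and exclude severe intercurrent conditions and serious active infection. Many patients with a Grade 3 screening event would never be dosed.

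This stands as a limit on size, and it makes the Step 4 figures upper values for the assumed rates. It does not close the gap. Protocol 9.3 collects AEs from consent, Protocol 9.2 expressly includes pre-dose SAEs, and SAP 7.1.2 provides for a pre-treatment class of AE.

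It is also fair that treatment-emergent incidence is tabulated and that one TEAE figure carries grades. The table shells are separate documents not available here, and they might separate the phases.

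A reader might infer more than the documents support:

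- *That the primary endpoint is contaminated.* The endpoint is "Evaluation of treatment-related AEs of BVD-523", which sits in the related and possibly related rows. Pre-dose events should not be there. One conditional route remains: if the worst-grade rule is applied before events are split by relationship, a pre-dose unrelated Grade 3 could lend its grade to an on-drug related Grade 1 of the same term. The SAP does not state the order, so this is an ambiguity and not a shown error.
- *That the MTD or RP2D is affected.* DLTs are limited to drug-related toxicity in the first 21 days of treatment, and the MTD follows from them. Protocol 3.1.4.3 names pharmacokinetics, pharmacodynamics and cumulative toxicity as possible support for the RP2D. SAP 12 plans a Part 1 safety analysis to aid that discussion, but nothing ties the choice to the all-AE severity table.
- *That the discontinuation tables are distorted.* A patient who leaves before dosing because of a pre-dose event is not in the Safety Population, so a TEAE filter would change almost nothing there.

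**Conclusion.** The point holds as a reporting defect. The relationship and severity tables and the Part II bar graphs by relationship use a wider event set than the treatment period, and the treatment-emergent displays do not replace them. The effect falls on the severity table and the unrelated rows. The related and possibly related rows should change little, and the DLT counts and the MTD should not be disturbed.

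The size cannot be fixed from the documents. The Step 4 range rests on assumed rates, a constant hazard, full capture and no loss through eligibility. The 14-day column matches the planned screening window, and the 28-day column is the outer limit for consent. Incomplete capture makes the effect smaller, but it may also make it uneven across sites, because the schedule and Protocol 9.3 give different starting points.

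**What to change.** 1. In SAP 10.2 and SAP 14, base the relationship and severity tables and the related bar graphs on TEAEs, in both parts.
2. State that the worst-grade and strongest-relationship rule is applied to treatment-emergent events only, and say whether it is applied before or after events are split by relationship.
3. Add to the TEAE definition that an event present before the first dose which worsens on drug counts as treatment-emergent. The current definition is a date window with no worsening clause, so a bare filter on onset date could drop a real on-drug toxicity recorded as one continuing event.
4. Put purely pre-dose AEs in a separate listing.
5. Reconcile the schedule of assessments, which has no AE mark at screening, with Protocol 9.3, which collects from consent.

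The cost is SAP wording and minor reprogramming. The date window and the phase classification are already in the SAP (10.2 and 7.1.2), although the worsening clause needs a rule for changes of grade. The downside is that purely pre-dose events would no longer appear in the relationship and severity tables or their graphs, where some readers may look for them.

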10.3 SERIOUS ADVERSE EVENTS AND DEATH

Separate data listings and summaries will be presented for all SAEs and deaths.

10.4 LABORATORY EVALUATIONS

Laboratory evaluations obtained from the following clinical laboratory tests will be collected at Screening, Baseline, Days 8, 15, 22, 29, 36, 43, and, in patients who continue treatment, every 3 weeks or if clinically indicated thereafter:

- **Hematology** – hemoglobin, hematocrit, white blood cells (WBC) count with differential, red blood cells (RBC) count, erythrocyte sedimentation rate (ESR), and platelet count.
- **Blood Chemistry** – albumin, alkaline phosphatase (ALP), total bilirubin, calcium, chloride, creatinine, creatinine clearance, glucose, inorganic phosphorus, potassium, total protein, alanine aminotransferase (ALT), aspartate aminotransferase (AST), C-reactive protein (CRP), Lactic dehydrogenase (LDH), sodium, blood urea nitrogen (BUN), and uric acid.
 - If the total bilirubin concentration is increased above 1.5 times the upper normal limit, total bilirubin should be differentiated into the direct and indirect reacting bilirubin.
 - Cholesterol, HDL, LDL, and triglycerides levels will be measured at Screening and first day of each cycle only.
- **Urinalysis** – specific gravity, pH, semi-quantitative “dipstick” evaluation of glucose, protein, bilirubin, ketones, leukocytes, and blood. Abnormal findings by dipstick will trigger a full microscopic examination including RBC, WBC, and casts.

Results of all evaluations (normal, abnormal clinically significant, abnormal not clinically significant, not done) from each laboratory test will be tabulated by study visit and treatment group for each study part. A listing of all laboratory evaluations and abnormal clinically significant laboratory evaluations will also be provided.

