#### Tissue Mineralization

Tissue mineralization has been observed in rodent toxicology studies of BVD-523. The incidence and severity of mineralization was dose-dependent and effects were observed in 1 or more tissues at toxic doses. In animals in which mineralization occurred after treatment

with BVD-523, significantly increased serum phosphorus and modestly decreased serum calcium were seen; these effects were not observed in animals in which there was no mineralization.

Tissue mineralization has been reported in rodents with other compounds that target the MAPK pathway and published studies suggest that the MAPK pathway is a negative regulator of matrix mineralization both *in vitro* and *in vivo*.

Routine clinical laboratory tests, including blood chemistry analyses for calcium and inorganic phosphate, will be performed and any indication of abnormalities may result in further investigations. A clinical monitoring strategy similar to this was previously employed for related drugs that target the MAPK pathway.

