to 14 days at dose levels up to 100 mg/kg twice daily; and for up to 5 days at dose levels up to 150 mg/kg/dose once daily. The incidence and severity of mineralization seen in these studies was dose-dependent and effects were observed in 1 or more tissues at toxic doses. In animals in which mineralization occurred after treatment with BVD-523, significantly increased serum phosphorus and modestly decreased serum calcium were seen; these effects were not observed in animals in which there was no mineralization. Therefore, the risk of tissue mineralization can be assessed by serum phosphorus and calcium monitoring. A clinical monitoring strategy similar to this was previously employed for related drugs that target the MAPK pathway because those compounds likewise elicited mineralization in rodents.

When BVD-523 was administered to male and female Sprague-Dawley rats for up to 28 days at a dose level of 25 or 50 mg/kg twice daily, it was poorly tolerated. Although most clinical signs and clinical pathology findings reversed following 4 weeks of recovery, skin lesions and histopathology findings persisted in many tissues at both dose levels after the recovery phase. Based on these findings, 25 and 50 mg/kg twice daily dose levels were considered severely toxic. Administration of 12.5 mg/kg twice daily for 28 days was generally well-tolerated by rats of both sexes; however, this dose level was associated with test article-related findings that included: swelling in the neck; decreased forelimb strength; multiple clinical pathology findings; enlarged lymph nodes, spleen, and mammary gland. Based on these findings, the severely toxic dose in 10% of the animals (STD10) for BVD-523 when administered for up to 28 days in Sprague-Dawley rats is 12.5 mg/kg given twice daily (25 mg/kg/day). On Day 28 of the dosing phase, this dose level corresponded with a  $C_{max}$  of 28700 and 15323 ng/mL and  $AUC_{0-12}$  of 264868 and 124341 hr.ng/mL for males and females, respectively.

BVD-523 was administered to male and female beagle dogs for up to 28 days at dose levels of 15, 5, or 2 mg/kg twice daily. Initial analysis of the toxicity profile observed shows that BVD-523 was well tolerated in dogs. The rat was designated the most sensitive species and rat data were used to calculate the starting dose in man.

BVD-523 has a measured UV absorbance at 320 nm, which means that it can absorb both UV-A and UV-B. BVD-523 may therefore act as a photosensitizing agent in man.

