Blood chemistry will be analyzed at each trial center by a certified laboratory and a report of the laboratory values will be sent to the trial center. The investigator will review the laboratory reports before dosing and appropriate action taken to address any clinically significant abnormal values. Laboratory parameters for which clinically significant values are noted will be re-measured on the appropriate clinical follow-up arranged by the investigator. Values will be monitored until stabilized, or the laboratory value returns to a clinically acceptable range (regardless of relationship to study medication). Any laboratory value that remains abnormal at the end-of-study (EOS) and that is considered clinically significant will be followed according to accepted medical standards for up to 30 days or until resolution of the abnormality.

Ophthalmologic examinations include best-corrected visual acuity, visual field examination intraocular pressure, external eye examination, and dilated funduscopy. For additional details refer to study manual).

Toxicity will be assessed using the National Cancer Institute Common Terminology Criteria for Adverse Events, version 4.03.

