10.5 VITAL SIGNS

Descriptive statistics for systolic blood pressure (mm Hg) diastolic blood pressure (mm Hg), pulse rate (bpm), temperature (°C), height (cm), and weight (kg) will be presented by study visit and treatment group visit for each study part. Also, changes in these vital signs from baseline to each subsequent visit will be tabulated by dose level/treatment group for each study part. Note that height is only collected at Screening and weight is only collected at Screening and at the beginning of each cycle of treatment.

A listing of vital signs will also be provided.

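### The laboratory tables planned in SAP 10.4 show neither the direction nor the size of a change from baseline

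*SAP*

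**What the plan says.** SAP 10.4 gives one rule for all hematology, chemistry and urinalysis tests. In each study part, every result is counted per visit and per treatment group in one of four categories: "normal, abnormal clinically significant, abnormal not clinically significant, not done". The only other output is listings: "A listing of all laboratory evaluations and abnormal clinically significant laboratory evaluations will also be provided". The section calls for no mean or median, change from baseline, high/low split, shift table or graded laboratory table. SAP 14 names one hematology, one chemistry and one urinalysis table per part. The table shells are separate documents and are not part of the text reviewed here.

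Other numeric safety data are treated differently. For vital signs, SAP 10.5 plans descriptive statistics, and "changes in these vital signs from baseline to each subsequent visit will be tabulated". SAP 10.6 summarizes ECG parameters as values and as changes, limiting cohort summaries to cohorts of at least 3 patients. SAP 6.6 defines descriptive statistics for continuous data and SAP 7.3 defines change from baseline. SAP 10.4 uses neither.

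Protocol 1.4 (Tissue Mineralization) reports that in affected animals "significantly increased serum phosphorus and modestly decreased serum calcium were seen". Protocol 1.4.3 concludes that "the risk of tissue mineralization can be assessed by serum phosphorus and calcium monitoring". Protocol 6.5 adds that "Blood chemistry will be analyzed at each trial center by a certified laboratory".

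**The concern.** Safety and tolerability is the primary objective, and two kinds of laboratory change matter particularly in this trial.

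- **Phosphorus and calcium.** The animal signal has a direction for each analyte: phosphorus up, calcium down. The planned table has no direction.
- **AST, ALT and creatinine.** Protocol 1.4 already reports drug-related elevations, from mild to severe. Patients may enter with abnormal values, so what matters is how far they move from baseline. The DLT definition itself refers to a doubling of AST/ALT from a grade 2 baseline, which a category count cannot express.

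The same four categories are used in SAP 10.8 for physical examination findings, where there is no number to summarize. Applied to laboratory tests, they discard numbers that have been collected. At stake is whether someone reading the laboratory tables, rather than the listings, can see which way an analyte moved and by how much, by dose level or group.

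**Working it through.** The plan states no figure on this point, so there is none to reproduce. The check asks what the planned table can and cannot return.

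**1. Direction.** At a given visit, let h patients be above the local range and l below it. The table splits abnormal results by clinical significance, not by side, so abnormal (both kinds) = h + l. Exchanging h and l leaves the total unchanged. A rise in phosphorus and a fall affecting the same number of patients look the same if the significance ratings are the same.

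**2. Worsening from an abnormal baseline.** Inputs are from Protocol 4.3: AST and ALT up to 3 times ULN, or 5 times with liver involvement; creatinine up to 1.5 times ULN, or a GFR of at least 50 mL/min. Take a doubling from each limit:

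| Analyte | Entry limit (x ULN) | After doubling (x ULN) | Normal/abnormal at both times |
|---|---|---|---|
| AST/ALT | 3 | 2 x 3 = 6 | abnormal |
| AST/ALT, liver involvement | 5 | 2 x 5 = 10 | abnormal |
| Creatinine | 1.5 | 2 x 1.5 = 3 | abnormal |

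The only possible movement is from not clinically significant to clinically significant, and SAP 10.4 gives no numerical threshold for that.

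**3. No link within patient.** The tables are counts per visit. If a patients move from normal to abnormal and b move back, the count changes by a - b. When a = b it does not change at all. A baseline-to-worst shift table shows a and b separately.

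**4. What numeric summaries would add.** Assumptions, not in the documents: equal SD at both times and within-patient correlation rho of 0.3 to 0.7. The standard error of a mean paired change, in baseline SD units, is sqrt(2(1 - rho)/n).

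| n | rho = 0.3 | rho = 0.5 | rho = 0.7 |
|---|---|---|---|
| 3 | sqrt(1.4/3) = 0.68 | sqrt(1.0/3) = 0.58 | sqrt(0.6/3) = 0.45 |
| 15 | sqrt(1.4/15) = 0.31 | sqrt(1.0/15) = 0.26 | sqrt(0.6/15) = 0.20 |

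In a Part 2 group of 15, a mean change is moderately precise and keeps its sign. In a cohort of 3 it is only descriptive.

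**5. Why a mean is not enough.** The protocol says the phosphorus and calcium changes were absent in animals without mineralization, so the signal may sit in a few patients. If one patient in 15 rises by 2 SD, the group mean moves by 2/15 = 0.13 SD, less than the smallest standard error above (0.20). A shift table would show that patient if the value crosses a range limit or a grade. Shift tables should therefore come first, with descriptive statistics as the supplement.

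**The case against.** The strongest reply is that the trial does not depend on this table to find toxicity, and most of that reply stands.

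- **Monitoring is patient by patient.** Under Protocol 1.4, abnormal calcium or phosphate may lead to further investigation. Under Protocol 6.5, the investigator reviews reports before dosing and follows significant values. SAP 10.4 alters none of this.
- **Values are kept.** SAP 14 has full listings for each panel, and separate ones for clinically significant abnormalities. In a one-patient cohort a listing is all that is needed.
- **There is a second route.** An abnormal laboratory finding can be an adverse event (Protocol 9.1). Adverse events are graded and tabulated by severity and relationship, and DLTs have their own tables. This depends on the finding being reported as an event and does not cover drift below that threshold.
- **Some facts are unseen.** The table shells could contain more, and Protocol 10.3.8 promises laboratory summaries without fixing their form. SAP 10.4 does not say who assigns the categories; that the investigator does so is an inference from Protocol 6.5.

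A reader might go further and infer that the tables cannot show a mineralization signal, or that laboratory drift would be largely invisible. The documents do not support that. They call the phosphorus rise significant, and a large rise would increase the abnormal count, though without direction.

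A reader might also assume a reference range of +/-2 SD and a 1-SD rise in every patient. That moves 2.3% to 15.9% above the upper limit and leaves about 84% at or below it. Neither assumption is in the documents, and a uniform rise conflicts with changes confined to affected animals. Even on those figures the count above the limit rises about sevenfold (15.9/2.3 = 6.9).

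None of these replies supplies an aggregate laboratory summary with direction and size.

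**Conclusion.** The concern holds as a gap in the aggregate laboratory summary. The planned tables cannot separate high from low, cannot reliably show worsening in patients already abnormal at entry, and do not link a patient's baseline to later values. These conclusions follow from the text of SAP 10.4 and Protocol 4.3 and need no distributional assumption. They do assume that the stand-alone shells add nothing beyond the SAP text.

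The consequence is limited. Patient-level detection is unaffected, no data are lost, and the definitions of DLT, MTD and RP2D do not change. What suffers is the laboratory evidence that a reader of the safety tables can use, in a trial whose primary objective is safety. The documents do not allow the loss to be expressed as a number of missed patients; the standard errors above only illustrate what numeric summaries could offer.

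**What to change.** Amend SAP 10.4 and the matching entries in SAP 14:

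1. Add shift tables from baseline to worst post-baseline value, by dose level or group. Use CTCAE grade, or low/normal/high against the local range where no grade applies. Cover at least calcium, inorganic phosphorus, creatinine, AST and ALT, keeping high and low separate.
2. Add descriptive statistics (SAP 6.6) and change from baseline (SAP 7.3) by visit for numeric analytes, in cohorts of at least 3 patients. SAP 10.6 already sets that limit for ECG.
3. State how units from local laboratories are standardized, and whether calcium is corrected for albumin, which is already collected.

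The existing category tables and listings can stay. The cost is a few more tables and the unit standardization across up to 15 sites. Grades based on ULN will still depend on local ranges, so that source of variation remains. No new samples, visits or procedures are needed, and no clinical rule changes.
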